4.5 Screening

All potential participants (whether recruited online or in-person) will complete an online screening survey to obtain consent/assent to be screened and verify all inclusion criteria. Screening may occur on the same day as enrollment or beforehand. The online screening survey will begin with a script that will be read by participants to explain the purpose of screening and clarify that if they are eligible, they will be invited to participate in the study. The script will also provide general information about the research

study, the nature of the screening questions and related potential risks, the approximate length of the screening (~5 minutes), the confidentiality of the screening information, the use of any screening information obtained, the ability to skip any questions or withdraw at any time, and contact information of key study personnel. After reading this screening script, participants will be asked if they are interested in participating and agree to voluntarily complete the screening procedure. Participants will electronically indicate their agreement and then take the survey. The study will use SSL encryption for transfers of information online and data will be stored in the secure, HIPAA-compliant servers of SurveyGizmo. The Emory AC team maintains a business partner HIPAA agreement with SurveyGizmo.

For potential participants who are at least 15 years of age, the survey will ask for the first name, e-mail, and phone number of the participant. Potential participants who do not meet eligibility criteria will be asked if they would like to be contacted about other research studies. Upon completion of enrollment, potential participants who are ineligible or do not enroll in the study and decline further contact will have their contact information destroyed.

The Analytic Core will securely share the contact information of eligible participants with SRV sites via a secure iTech Box account. SRV staff will enter the eligible participant into SMART (described in more detail later in the protocol) for scheduling and contact participants to schedule an in-person visit at the SRV. SRVs will also have the option to have the participant complete the online screener the day of the in-person visit; study staff can view eligibility on the browser window once the screener is complete or review the automatic eligibility email sent after survey completion.

5.0 STUDY PROCEDURES

5.1 Enrollment procedures

Individuals who screen eligible will be contacted and scheduled for an in-person visit to the SRV at the participant's earliest convenience. SRVs will also have the option to have the participant complete the online screener the day of the visit. During the visit, the eligibility of the participant will be confirmed, details of the study will be explained and informed consent/assent obtained.

Individuals who do not consent or assent to participate will be asked if they are willing to provide their reason for declining participation; responses will be recorded on a CRF. Individuals assessed as ineligible for enrollment will have the reason(s) for ineligibility recorded.

The study team may request tabulated information on individuals who participated in the enrollment process, but did not provide informed consent/assent and the reasons these individuals refused to participate. These data will provide general information on the population that is recruited at the SRVs into the study

After informed consent/assent is obtained, the participant will complete a CASI baseline assessment. For Aim 3, randomization will only occur AFTER a baseline assessment is completed.

In Aim 3, participants assigned to the intervention group will be considered enrolled in the study after they have completed the baseline assessment, been randomized, and completed app onboarding (for

the intervention arm). Participants assigned to the control arm will be considered enrolled in the study after they have completed the baseline assessment, been randomized, and been given standard of care materials.

CRFs will be completed by study staff to capture the participant's eligibility and enrollment.

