- SAMPLE SIZE:** *Aim 1 will include approximately 40 HIV-uninfected young men who have sex with men (YMSM). Aim 2 will include up to 15 YMSM. Aim 3 will enroll 60 YMSM, with 40 YMSM randomized to receive LYNX, and 20 YMSM randomized to receive standard of care. Total sample size for this project will be up to 115 YMSM.*
- POPULATION:** *HIV-uninfected YMSM between the ages of 15-24, assigned male sex at birth and male-identified, enrolled at two study sites in Chicago, IL and Tampa, FL.*
- STRATIFICATION:** *Participants in the pilot RCT will be randomized 2:1 to receive the LYNX app (N=40) vs. standard of care (N=20)*
- DATA COLLECTION:** *Data in the formative phase (aim 1) will include videotaped focus groups and in-depth interviews with YMSM. Data from the technical pilot (aim 2) will include an online qualitative exit interview, a computer-assisted self-interview (CASI), and app analytics. Data from the pilot RCT (aim 3) will include CASI, app analytics, case-report form (CRF) data on study implementation, and in-depth interviews in up to 20 participants in the LYNX arm.*
- OBJECTIVES**
- 1) To conduct qualitative, formative work to refine a mobile phone app, LYNX, to promote HIV/STI testing and PrEP uptake among YMSM*
 - 2) To conduct a technical pilot to optimize LYNX app functionality, technical performance, and user satisfaction*
 - 3) To conduct a pilot RCT to evaluate the feasibility and acceptability of LYNX to increase HIV/STI testing and PrEP uptake among YMSM*

Study Design or Schema

Figure 1: Study overview

[figure not shown]
[figure not shown]

Figure 2: Phase 3, RCT Pilot Study Schema

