3.0 STUDY DESIGN

Using an iterative process of app development, this study will be conducted in 3 phases: 1) formative research to refine LYNX with input from YMSM; 2) a technical open pilot to optimize functionality and technical performance; and 3) a pilot RCT to evaluate feasibility, acceptability, and preliminary efficacy of LYNX.

- **Formative Phase**

Guided by the IMB model, the LYNX app will be refined through an iterative design process informed by a series of focus groups and in-depth interviews in up to 40 YMSM to elicit feedback on content, usability, layout, and functionality of the LYNX app.

- **Technical Pilot**

The LYNX app will be tested in a 2 month technical pilot study in up to 15 YMSM to optimize app functionality and performance. Data will be used to further refine the app and finalize the intervention protocol, outcome measures, and assessment tools for the pilot RCT.

- **Pilot RCT**

60 HIV-uninfected YMSM will be enrolled into a 6 month pilot study evaluating the feasibility and acceptability of the LYNX app. Participants will be randomized 2:1 to receive the LYNX app or a standard of care control condition. Feasibility and acceptability will be assessed through app analytics of usage patterns (logins, use of app components) and acceptability scales administered via computer-assisted self interview. We will also evaluate preliminary efficacy by comparing the proportion of YMSM who test at least once during the 6 month pilot, and proportion who successfully link to a PrEP provider, in the intervention versus control groups.

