5.2 Locator/Contact Information

Once the participant is consented, designated site study staff will complete a Contact Information Worksheet with the participant and/or enter the participant's contact information directly into SMART Web during the enrollment visit. Participants will also be asked to provide social media contact information, if the participant is willing. Participants will be asked to provide a working phone number or valid email address through which they can be reached. Participants will also be asked to provide valid contact information for a family member and/or friend who can be called in the event the participant cannot be reached by phone or email. Participants will be asked if messages can be left at the numbers provided. Study staff will not leave messages unless expressly permitted to do so by the participant which also will be documented on this form. If permission is given to leave messages, site study staff will assure participants that messages left with a family member or friend will only ask the participant to contact study staff and will not include any protected health information or information related to study participation.

The Contact Information Worksheet will not contain any study data and will be entered into the SMART system and maintained under double locks at the study site, separate from all study records, with access limited to designated site research personnel.

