5.4.3 Pilot RCT (Aim 3)

5.4.3.1 Screening and Enrollment

Potentially eligible participants will attend an enrollment visit where eligibility is confirmed, the details of the study will be explained, and informed consent obtained. Participants who participated in formative and/or technical pilot phases of this study will not be allowed to participate in the pilot RCT. Eligible participants will complete a baseline computer assisted self-interview (CASI) of HIV risk behavior, HIV/STI knowledge, utilization of STI/HIV prevention services, PrEP knowledge and attitudes, psychosocial measures (including depression, substance use, stigma, social support), and HIV risk perception and will be enrolled in the study on the same day if possible. Participants will be randomized to receive LYNX (intervention) vs. the standard of care (control) in a 2:1 ratio (see randomization procedures in section 5.2). This design was chosen to maximize collection of acceptability data among app users. Participants who have completed the baseline assessment, have been randomized, and complete app onboarding (intervention arm) or receive the standard of care information about HIV/STI testing and PrEP (control arm) will be considered enrolled in the study. All enrolled participants will receive counseling on the importance of HIV testing per local testing guidelines.

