5.4.3.4 Study Follow-up

All enrolled participants will be followed for 24 weeks. After enrollment, all follow-up visits will occur online, with SMS reminders, email, and phone follow-up conducted as needed to ensure completion of study procedures. Participants will complete an online CASI at 12 and 24 weeks and receive a stipend for completion of procedures at each study visit. Visit windows will be approximately 14 days before/after the target date. Participants will also be able to obtain additional home HIV self-test kits during the study follow-up, if needed. At the 3 month visit, any persons who have a positive HIV test plus up to 20 participants randomized to the LYNX arm will participate in an in-depth interview conducted by UCSF/SFDPH study staff via video-conferencing. The purpose of this interview is to elicit feedback on their experiences using the app, any technical difficulties encountered, and how the app could be further improved. Participants will be selected for interviews using purposive sampling based on level of engagement with the app, whether participants completed HIV/STI testing and/or initiated PrEP during the study, and to achieve diversity based on sociodemographics (e.g. age, race/ethnicity). Additionally, we will offer interviews to all participants who have a confirmed HIV diagnosis. In addition to asking about their experiences using the app, these participants will also be asked about additional information or support that would have been helpful at the time of receiving a positive HIV test result, and their experiences in getting linked to HIV care. By purposively sampling certain participants for the exit interviews, the goal is to select "information-rich cases from which one can learn a great deal about issues of central importance to the purpose of the research."⁵¹ All interviews will be audio recorded for transcription and analysis. Participants will be reimbursed for completion of each study visit according to local study site guidelines.

We will also conduct medical record abstraction for participants in this study. The goal of the medical record abstraction is to explore whether it is feasible to collect more objective measures of HIV and STI

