6.3.4 Premature Discontinuation/Off-Study evaluations/measures

Participants enrolled in the pilot RCT who discontinue study participation after the Baseline visit, but prior to the completion of the final study visit, will complete a Premature Study Discontinuation visit within four weeks after the decision to prematurely discontinue from the study is made and will include all week 24 visit procedures as appropriate.

The principal investigator has the authority to withdraw any participant at any time if it his/her opinion that it would be in the best interest of the participant. The participant will be informed of this withdrawal and explained the rationale. Withdrawal will be documented in the study tracking system.

Participants will be prematurely discontinued from the study if any of the following occurs:

- The participant withdraws consent/assent;
- The participant is unwilling or unable to comply with study procedures;
- The investigator believes that ongoing participation may cause harm to the participant or study staff;
- The investigator believes that ongoing participation may impact the integrity of the study data;
- The study is cancelled by the NIH (or iTech, or other administrative entity);
- The study is cancelled for other administrative reasons; or
- Death of the subject

Subjects who are prematurely discontinued from the study may be allowed to re-enroll into the study on a casebycase basis. The Protocol Team will review the number of slots opened for replacements on a monthly basis, or more frequently, as needed.

Participants who seroconvert during the study enrollment will not be discontinued from the study and

will continue to have access to the app and its functions.

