8.0 PARTICIPANT MANAGEMENT

8.1 Tracking Participants/Follow-up

All subjects will be contacted up to 2 weeks prior to their target date for a follow-up visit to complete study visit procedures; additional reminders will be provided on/after the target date as needed to ensure completion of study visit procedures. Multiple contact methods will be used for youth who are difficult to reach (e.g., mail, alternate phone numbers, e-mail, text message, social media contact information). Subjects will be asked whether or not messages can be left for each of the phone numbers that they provide. They will be informed that messages will not contain any information regarding the nature of the project.

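### The primary feasibility pass mark differs between 6.3.3 and 10.1.3, and Aim 3 enrolment is defined after randomisation with no rule that testing and PrEP uptake are analysed for everyone randomised

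*Combined protocol and SAP*

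**What the plan says.** **Feasibility pass mark.** Section 6.3.3 marks app opening as a primary endpoint. It is met if 60% or more of those randomised to the intervention open the app at least once after staff introduce it. Section 10.1.3 sets the minimum criterion as a point estimate strictly above 0.60 and gives no denominator. Section 1.1 makes the later efficacy trial conditional on LYNX being found feasible and acceptable.

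**Enrolment.** In section 5.1, participants assigned to LYNX are "considered enrolled in the study after they have completed the baseline assessment, been randomized, and completed app onboarding". Control participants count once they have completed the baseline assessment, been randomised and been handed the standard-of-care materials. Section 5.4.3.1 repeats the rule: participants must "complete app onboarding (intervention arm) or receive the standard of care information".

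**Follow-up.** Section 5.4.3.4 states "All enrolled participants will be followed for 24 weeks". The discontinuation visit in 6.3.4 is for "Participants enrolled in the pilot RCT who discontinue study participation after the Baseline visit". Two passages reach wider. Section 5.2 takes contact details early ("Once the participant is consented, designated site study staff will complete a Contact Information Worksheet"), and section 8.1 says "All subjects will be contacted up to 2 weeks prior to their target date".

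**Target.** The abstract says "Aim 3 will enroll 60 YMSM, with 40 YMSM randomized to receive LYNX" and section 3.0 says "60 HIV-uninfected YMSM will be enrolled into a 6 month pilot study". Sections 5.3 and 10.1.3 give the same 60 as randomised.

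**Analysis.** Section 10.1.3 evaluates testing and PrEP uptake by unadjusted risk ratios and names no analysis population. Section 10.2 refers to study participants without saying whether a man randomised but not yet enrolled is one.

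**The concern.** A pass mark that decides a primary endpoint should have one value. Here a result of exactly 60% would be declared feasible under one section and not under the other, and the choice could be made after the count is known.

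The enrolment rule is a different kind of problem. Randomisation protects the comparison only if everyone randomised stays in it. Here a man enters the trial, as the protocol defines it, only after a later step, and that step differs by arm: a LYNX man completes onboarding, a control man is handed materials. If the site or the analyst takes enrolled participants as the set to follow and compare, men can drop out of the comparison after their allocation is known, at different rates and for different reasons in each arm. Those who miss the step may be less engaged and less likely to test or start PrEP.

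**Working it through.** **The plan's own figure.** Section 10.1.3 gives 37 to 42 points as detectable with 80% power, from 60 randomised 2:1 with 10-20% attrition. That leaves 36 v 18 or 32 v 16. Alpha and control rates are not stated; I assume two-sided 0.05 and control rates of 10-50%. The detectable difference d solves

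d = 1.96·√[p̄(1−p̄)(1/n₁+1/n₀)] + 0.842·√[p₁(1−p₁)/n₁ + p₀(1−p₀)/n₀], where p₁ = p₀ + d and p̄ is the pooled rate.

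This gives about 36 to 39 points at 36 v 18 and 37.6 to 41.5 at 32 v 16, so the stated range is reproduced. It starts from 60 randomised, so analysing all randomised does not disturb it.

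**Pass mark.** With n = 40 randomised to LYNX (5.3), 60% or more needs 24 openers and strictly more than 0.60 needs 25. The rules differ only at X = 24. With X ~ Binomial(40, p):

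| True opening rate p | P(X ≥ 24) | P(X ≥ 25) | P(X = 24) |
|---|---|---|---|
| 55% | 31.9% | 21.4% | 10.4% |
| 60% | 56.8% | 44.0% | 12.8% |
| 65% | 79.8% | 69.5% | 10.3% |
| 70% | 93.7% | 88.5% | 5.2% |
| 80% | 99.9% | 99.7% | 0.2% |

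**Leaving out LYNX men who are not onboarded.** The documents give no onboarding failure rate and no expected testing rate, so both are assumed, with no true effect and, at first, no loss in control. Let k of 40 LYNX men be left out, let them test at rate q, and let the overall rate be p:

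r = (40p − kq)/(40 − k), and apparent RR = r/p.

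| Left-out men test at | k = 2: RR (shift at p = 30%) | k = 4: RR (shift at p = 30%) |
|---|---|---|
| the usual rate | 1.00 (0) | 1.00 (0) |
| half the usual rate | 1.03 (0.8 points) | 1.06 (1.7 points) |
| zero | 1.05 (1.6 points) | 1.11 (3.3 points) |

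For scale, the 95% half-width for 40 v 20 at 30% is 1.96·√[0.3·0.7·(1/40+1/20)] = 0.246, about 25 points.

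The two-sided false-positive rate, by exact enumeration of a pooled z-test at p = 30%, is 5.1% with nobody left out. It is 5.1% (k = 2) and 5.6% (k = 4) when never-testers are left out, and 5.0% and 5.1% when half-rate testers are. The highest value seen with k = 4 never-testers is 7.0%, at p = 50%, against 5.5% with nobody left out.

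**Allowing loss in control.** If never-testers are also lost before receiving materials:

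- 2/40 LYNX and 1/20 control: (40/38)/(20/19) = 1.00
- 4/40 and 2/20: (40/36)/(20/18) = 1.00
- 2/40 and 2/20: (40/38)/(20/18) = 0.95

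The sign therefore depends on which arm loses more, and on how those men would have behaved.

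**The case against.** A reader might infer that the plan excludes men who are not onboarded and so tilts the efficacy comparison towards LYNX. The documents do not support that. Nothing says these men are dropped; 5.4.3.4 says all enrolled, not only enrolled. Contact details are held from consent, 8.1 can be read as covering everyone randomised, and 7.4.1 has CRFs record randomisation assignment. The abstract uses enrolled and randomised almost interchangeably, 2.2 compares arms, and the 6.3.3 denominator is already as randomised. Nor is the direction fixed. Control also has a step after randomisation, and because 5.3 requires interest in using LYNX, a man allocated to control could leave before it. All of this stands. What remains is that no section states an as-assigned analysis for testing and PrEP uptake.

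The effect is also small. Section 4.2 excludes men unwilling or unable to download the app, 5.4.3.2 has staff walk participants through onboarding, and 5.6 adds a checklist. The outcome is secondary, and 10.1.3 already asks for careful interpretation. This stands too; it limits the size but does not supply the missing rule.

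On the pass mark, the rules disagree at a single count, and the chance of hitting it falls to 5% at a true rate of 70% and 0.2% at 80%. That is right, but the conflict matters most near the threshold, where the decision is hardest.

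**Conclusion.** **Pass mark: wrong as written.** Two sections give incompatible thresholds for a primary endpoint on which progression depends. With 40 randomised, the outcome is contradictory at 24 openers, which has a 10-13% chance for true opening rates of 55-65% and little chance well above that.

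**Enrolment and analysis set: a gap, not a demonstrated bias.** Enrolment follows randomisation with an arm-specific condition, follow-up is tied mainly to enrolment, and the analysis set for the secondary outcomes is unstated. If men who miss the step are left out, selection bias becomes possible. It would favour LYNX if the loss is mainly in LYNX and those men test less; with comparable or greater proportional loss in control it vanishes or reverses. Under the assumptions shown, the risk ratio moves to 1.03-1.11, or 0.8 to 3.3 points at a 30% testing rate, against a half-width of about 25 points and a detectable difference of 37-42. That would not by itself change how this pilot is read. It is still worth closing, because the remedy is nearly free and is best settled before any results are seen.

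**What to change.** 1. Use one feasibility threshold in 6.3.3 and 10.1.3, and state the 6.3.3 denominator (all randomised to LYNX) in both. Count men not onboarded as not having opened the app.
2. In 5.1, 5.4.3.1 and 5.4.3.4, count participants as in the trial from randomisation in both arms, and follow everyone randomised for 24 weeks whether or not the later step was completed. Record completion of onboarding or receipt of materials as a process measure.
3. State the target of 60 as randomised throughout, including the abstract and 3.0.
4. In 10.1.3, state that testing and PrEP uptake are analysed for all randomised participants in their assigned arm, with missing outcomes handled under 10.2.

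The cost is protocol wording and follow-up of perhaps a few more men, whose contact details are already held. Completion and app-opening rates may come out slightly lower. The sample size and the stated detectable difference do not change.
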